Over time, cumulative clinical trial experience has revealed that a variety of alterations to the stimulation protocols, delivering different doses and timing of stimulation, can produce beneficial antidepressant effect without jeopardizing safety.¹⁰ In 2016, FDA cleared a new treatment protocol termed “Dash”. The Dash protocol was introduced to improve the acceptability and convenience of TMS therapy by reducing the duration of a 3000-pulse session to as short as 18.75 minutes, which is half the time required for the Standard protocol FDA cleared in 2008.

In 2021, several optional features were added to the NeuroStar TMS system including a feature called “SoftStart”. When enabled, SoftStart introduces a series of stepped pulses within each pulse train which alters the pulse magnitude during the beginning and ending of a treatment pulse train. The pulse train gradually increases (ramps up) in magnitude (MT Level) until the prescribed MT treatment level has been obtained. At the conclusion of the 40 pulses in the train at the prescribed MT level, a series of pulses ramp down before the intertrain interval rest period begins. For some patients, sensitivity at the treatment site can cause discomfort and studies have been conducted to investigate ways to improve patient comfort and prevent dropout due to intolerance of treatment.²¹ Patient intolerance can not only increase drop-out but also prevent patients from reaching the prescribed dose or reduce the number of treatments delivered at the prescribed dose. For accurate, safe, and effective application of brain stimulation, it is essential that an appropriate level of electric current be induced within a target region. Under stimulation reduces the probability of detecting significant results and deprives patients of necessary treatment dosages.²⁰ By ramping pulses from 60% to 100% of the programmed treatment level, SoftStart was designed to improve treatment comfort, which could also allow patients to reach the prescribed treatment intensity more easily or reach that intensity in a shorter time which will provide patients with a greater percentage of their pulses at the full prescribed dose.

The objective of this study is to evaluate the effect of SoftStart on patient comfort when treated with TMS for major depression. The impact of SoftStart on the ability and the time taken to reach the prescribed dose of TMS and other secondary factors associated with patient comfort will also be evaluated.

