Since during the first few treatment sessions patients are typically ramped up to the desired treatment intensity (%MT) in a subjective manner by the treater, this process will be standardized during the study to minimize this confounding factor on perception of comfort. For all treatments, the first session will begin at 90% MT and the treater will ask the subject if they can tolerate the treatment intensity at 5 equal time intervals per treatment session (a treatment interval is 3 minutes and 45 seconds (3:45)). If tolerance is acceptable, the treater will increase the treatment intensity by 10% with the objective of reaching 120% by the end of the first treatment session. Dosage escalations during treatment will be limited to these 5 equal time intervals; however, dosage decreases can be done at any point due to patient intolerance. Treatment intensity changes will not be communicated to the subject. The treatment intensity achieved at each interval will be logged and documented in the study CRF. After the first interval (3:45), and after each stimulation session the subject will be asked to complete a "Comfort/Pain" VAS scale from (0-10cm). Once the subject completes the last 3:45 of a treatment session at 120%MT, they will begin their Crossover phase at the start of the next session. If a subject does not reach 120% MT by the end of the fifth treatment session, dose escalation attempts will continue, but they will transition to the Crossover phase. Refer to Attachment D for details of the Dose Escalation process.

Crossover Phase:

At the start of the 6th Treatment session or the session after the subject reaches the prescribed dose, the subject will be crossed over to the alternative treatment protocol and continue to alternate treatment each day for the next 3 treatments. Each day of these 4 treatment sessions,

at the first time interval (3:45) and the end of the session the subject will complete the comfort/pain questionnaire and be asked whether they preferred the current treatment, or the treatment received at the previous session (Todays Treatment, Last Treatment, No Difference).

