If the subject reaches the prescribed %MT at any of these visits and sustains that MT through the final 3:45 minute time interval, the next study visit will be the start of the crossover phase of the study (Crossover Treatment 1). If the subject does not achieve the prescribed MT by the end of the 5th Treatment session, they will continue to Crossover Treatment 1 at the next visit, however, attempts to achieve the prescribed %MT should continue and be documented.

Crossover Phase

Visit 1

Subjects will be crossed over to the alternative treatment protocol, those who had received treatment X will then receive treatment Y and vice versa. Subjects will start treatment at the %MT established in the previous session and all study treatment assessments completed on Treatment Visits 2-5 of the Ramp Phase will be repeated and documented for each visit of the Crossover Phase.

Visits 2-4

Subjects will be crossed over to the alternative treatment protocol, those who had received treatment X will then receive treatment Y and vice versa. At the start of treatment, subjects will start treatment at the %MT established in the previous session and all study treatment assessments completed on Crossover visit 1 will be repeated.

Visit 4: Final Crossover Visit

At the start of treatment for Crossover visit 4, subjects will be crossed over to the alternative treatment protocol, subjects will start treatment at the %MT established in the previous treatment and all study treatment assessments completed on Crossover visit 1 will be repeated.

At the end of the final treatment, the treatment protocol for further TMS sessions will be determined by the clinician and the patient as part of their normal care. The treatment choice will be documented, and the subject will be exited from the study. See subject flow diagram in section 14.2 for additional information.

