### **6.2 Analysis Populations**

*The following analysis populations are defined for analysis:*

1. **Intent-to-treat (ITT):** *The ITT population is defined as all subjects randomized.*
2. **Modified Intent-to-Treat (mITT):** *The mITT population is defined as all subjects in the ITT population where treatment was initiated.*
3. **Per protocol (PP):** *The PP population is defined as all subjects in with no significant protocol deviation, or adverse event that could compromise the validity of their assessments.*
4. **Safety (SAF):** *The SAF population is defined as all subjects that were exposed to any study device or treatment.*

The primary analysis set for efficacy endpoints and results will be the mITT set, with any other analysis sets defined as optional and supportive. The primary analysis set for safety endpoints and results will be the SAF set, with any other analysis sets defined as optional and supportive.

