### **6.6.2 Primary Efficacy Endpoints**

The Primary study outcome assessments will be determined based on differences in the mean VAS ratings on a 0-10cm VAS scale for comfort (the scale ranges from 0-100, and 0 = no pain or discomfort, and 100 = extreme discomfort or worst pain imaginable). Statistical methods employed to detect differences between the experimental and the control groups, for the below outcomes, may include a t-test, Chi-Square test, and Fisher's Exact test. Test for normality and equality of variances may be used for continuous parameters. If data are found to fail one or both, then nonparametric methods may be employed, eg, Wilcoxon Rank Sum test. For assessments including crossovers, a relevant method accounting for period effect, repeated measures, and randomized order may be utilized.

Analyses outlined below will be done for the average of patient scores.

One of the following analyses will be employed as the primary analysis of the primary efficacy endpoint:

Statistical Analysis Plan		Page 11 of 18
Sponsor Neuronetics	Study Comfort Start	Version 1.0

The difference in the change in Visual Analog Scale scores for Comfort after rTMS stimulation between treatments administered with the Dash protocol and with New feature enabled. Comfort will be evaluated as a change for all observations between groups, observations from Baseline to end of escalation phase, observations between groups during the crossover phase and observations within a patient between treatments in the cross-over phase.

At minute 3:45, and at the end of the treatment session, the subject will be asked to complete a Visual Analog Scale (VAS), for Comfort/Pain.

- a. All over group (throughout the whole trial, Ramp phase & Crossover phase) – all VAS scores for X → Y or Y → X (similar to 1.d.ii above. Start with the average of the 3:45, 18:45 scores on each Day for each subject, then average each of the daily X averages and average each of the daily Y averages for each patient, comparing the average of the 40 X averages to the average of the 40 Y averages, a one-sided hypothesis test evaluating if the “with Comfort Start” group, X, has lower average scores)

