- b. Between group comparison: Prior to cross over (reaching 120%MT): combination of the scores at 3:45 min and at the end of treatment, 18:45 min; (start with the average of the these two scores for each subject that reached 120% (average of all scores prior to & including 120%), then compare the average of the X averages (at most 20) to the average of the Y averages (at most 20), a one-sided hypothesis test evaluating if the “with Comfort Start” group, X, has lower average scores)
- a. Average of all the patient scores for all Crossover Phase treatments (start with the average of the 3:45 and 18:45 scores on each Crossover Day for each subject, then average each of the daily X averages and average each of the daily Y averages for each patient, comparing the average of the 40 X averages to the average of the 40 Y averages, a one-sided hypothesis test evaluating if the “with Comfort Start” group, X, has lower average scores)

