### **6.6.2.1 Primary Analysis**

The majority of the primary efficacy endpoints will be assessed with the following hypothesis:

$H_0$ : Comfort Start Dash is equal to or inferior to Dash

$H_a$ : Comfort Start Dash is superior to Dash

Statistical Analysis Plan		Page 12 of 18
Sponsor Neuronetics	Study Comfort Start	Version 1.0

Note that some of the hypothesis testing will be two-sided, but the majority of inferential statistical testing will be looking at a one-sided alternative hypothesis that the treatment protocol with Comfort Start employed is superior to the Dash protocol without Comfort Start employed.

The endpoints will be evaluated using the mITT population.

The primary endpoints will be assessed via descriptive (unless otherwise specified) and superiority statistics.

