### **6.6.3 Secondary Endpoints**

The secondary endpoints may be assessed via superiority or non-inferiority testing, with any non-inferiority margins to be defined, or may be assessed with descriptive summaries only.

The Secondary study outcomes will be determined as follows:

The ability to reach the prescribed treatment intensity, the time it takes to reach the prescribed intensity, maximum treatment intensity reached, subject treatment preference and discontinuations due to treatment discomfort between the two treatment protocols.

Once TMS therapy begins, adjustments to lower the stimulation intensity can begin immediately, as needed, for subject tolerance. The treater will assess if the subject can tolerate escalating the treatment MT by 10% at different time points. At each interval and the end of treatment, the treater will record the current %MT achieved. The goal will be to reach and sustain the target MT established by the treating physician of 120%MT. Once the target MT has been achieved and sustained for a certain period recording and increases of %MT may be discontinued but re-started at central intervals if %MT is subsequently reduced.

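### Candidate primary analysis (b) keeps only subjects who reached 120% MT, a post-randomisation outcome that treatment may change, and so contradicts the SAP's own mITT rule

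*SAP*

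**What the plan says.** SAP 6.6.2 does not fix the primary analysis: "One of the following analyses will be employed as the primary analysis of the primary efficacy endpoint". Three analyses are then worked out: one over the whole trial, one before crossover (item b), and one over the Crossover Phase. Item b compares the randomised groups on ramp-phase VAS with a one-sided test that SoftStart scores are lower. Its per-subject summary is the "average of the these two scores for each subject that reached 120% (average of all scores prior to & including 120"%), with at most 20 subjects per arm.

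The SAP's population rule is different. Section 6.6.2.1 states: "The endpoints will be evaluated using the mITT population". Section 6.2 states: "The mITT population is defined as all subjects in the ITT population where treatment was initiated". Protocol 18.2 analyses subjects with at least one post-treatment time point. None of these depends on the intensity reached.

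On how 120% MT is reached, Protocol 10.1 states: "If tolerance is acceptable, the treater will increase the treatment intensity by 10"%. Protocol 9.1 says SoftStart "could also allow patients to reach the prescribed treatment intensity more easily or reach that intensity in a shorter time". SAP 6.6.3 opens its list of secondary outcomes with: "The ability to reach the prescribed treatment intensity, the time it takes to reach the prescribed intensity". Protocol 13.1 keeps non-reachers in the study: "If the subject does not achieve the prescribed MT by the end of the 5th Treatment session, they will continue to Crossover Treatment 1".

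**The concern.** Subjects are randomised before the first stimulation. After that, reaching 120% MT depends on how well the subject tolerates treatment, as assessed by a treater who knows the assignment (Protocol 15.3). Tolerance is close to what the VAS measures. Item b therefore selects subjects on an outcome that is related to the endpoint and that the sponsor expects treatment to change. The two sets of reachers need not be comparable even though the randomised arms were.

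The direction of bias cannot be known in advance:

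- If non-reachers report more discomfort and Dash has more of them, Dash loses its worst scores and a real SoftStart benefit is understated.
- If SoftStart lowers reach, or if non-reachers score lower because their intensity was reduced, SoftStart is favoured.

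Protocol 13.1 gives the ramp phase the purpose of comparing comfort between treatment groups. Item b leaves out the subjects for whom comfort most limited treatment. If b becomes the primary analysis, its p-value no longer rests on randomisation.

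**Working it through.** **1. Who is in and who is out.** mITT is everyone randomised who started treatment. Item b is the subset who reached 120% MT. VAS is taken at 3:45 and at end of session in every ramp session (Protocol 8 and 13.1). A subject who never reaches target in five sessions can have 5 × 2 = 10 ramp scores, and item b uses none of them. A subject who reaches and sustains target at visit 1 contributes 2.

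**2. Inputs.** The plan has no figure to reproduce. It states no SD, effect size, reach rate or link between VAS and reach, and N = 40 is expressly not power-based (SAP 5). From the documents: 20 per arm, one-sided test. Assumed: 0–100 scale, true difference 10 points, SD 20 unless stated, one-sided level 0.05.

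**3. Bias formula.** Let a subject reach 120% MT when a latent intolerance score L falls below z(p), where p is the arm's reach rate, and let r = corr(VAS, L). Then

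E[VAS | reached] = μ − r·SD·φ(z_p)/p,

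and the bias in (Dash − SoftStart) is

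−r·SD·[φ(z_pD)/pD − φ(z_pX)/pX],

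with D for Dash and X for SoftStart. A negative value understates SoftStart.

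For reach 95% (X) and 75% (D): φ/p = 0.1031/0.95 = 0.1086 and 0.3178/0.75 = 0.4237, a difference of 0.3151. At r = 0.3 and SD 20 the bias is −0.3 × 20 × 0.3151 = −1.89.

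| Reach, SoftStart / Dash | r = 0.3 | r = 0.5 | r = 0.7 |
|---|---|---|---|
| 95% / 75% | −1.89 | −3.15 | −4.41 |
| 89.4% / 77.3% | −1.11 | −1.85 | −2.59 |
| 98% / 95% | −0.35 | −0.59 | −0.83 |
| equal | 0 | 0 | 0 |

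At 95% / 75%, varying SD from 15 (r = 0.3) to 25 (r = 0.7) gives −1.42 to −5.51. With r = −0.3 and SD 20 the bias is +1.89, in favour of SoftStart. The second row's reach rates are those implied by means 35 and 45, SD 20 and a VAS cut-off of 60: Φ(25/20) = 0.894 and Φ(15/20) = 0.773.

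**4. Extreme case: VAS alone decides reach.** With means 45 (Dash) and 35 (SoftStart), each arm truncated above a cut-off, the observed difference out of a true 10 is:

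| Cut-off | 55 | 60 | 65 | 70 |
|---|---|---|---|---|
| SD 15 | 6.30 | 7.25 | 8.12 | 8.83 |
| SD 20 | 5.57 | 6.30 | 7.02 | 7.71 |
| SD 25 | 5.14 | 5.71 | 6.30 | 6.88 |

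So 51–88% of the effect is retained.

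**5. Effect on the test.** Simulation of the model in step 3, 20 per arm, pooled t-test, 100,000 trials per row:

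| Scenario | r = 0.3 | r = 0.5 | r = 0.7 |
|---|---|---|---|
| No true difference, reach 75% SoftStart / 95% Dash: rejection | 8.5% | 11.7% | 16.3% |
| No true difference, reach 95% / 75%: rejection | about 3% | about 2% | about 1% |
| True 10 points, reach 95% / 75%: power | 31.5% | 26.1% | 21.4% |

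With all 20 per arm, a 10-point difference (0.5 SD) has 46.3% power by the noncentral t. Part of the drop is lost subjects rather than bias: with 20 × 0.95 = 19 and 20 × 0.75 = 15 subjects and no bias, the noncentrality is 0.5 × √(19 × 15/34) = 1.45, giving power of about 41%. With equal reach and no true difference, rejection stays at about 5%.

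**The case against.** Several points on the other side are fair.

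- **The size is assumed.** It runs from nothing (equal reach) through under one point (98% / 95%) to about five, with either sign. This stands, and it is why the claim is only that the restriction can bias.
- **The inflated false-positive rate needs SoftStart to reduce reach**, the opposite of the study's hypothesis. In the hypothesised direction, null rejection falls to about 1–3%. This also stands: the main expected risk is a missed or understated benefit rather than a false claim.
- **Item b may not be chosen, and the trial is exploratory.** True, but the SAP leaves the choice open and attaches a one-sided superiority test to item b. A trial run for planning purposes needs a trustworthy effect estimate.
- **It may be a drafting slip.** Item b treats crossing over and reaching 120% MT as one event, overlooking subjects moved on after session 5. That is plausible. As written, the text still excludes those subjects, and a slip is a reason to correct it.
- **If treatment affects neither comfort nor reach, the restricted test keeps its level.** Correct, but the validity of the test then depends on an assumption about reach that randomisation does not supply.

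**Conclusion.** The concern holds and should be fixed. Item b conditions a candidate primary analysis on a tolerance-driven event after randomisation, discards ramp scores that will have been collected, and contradicts SAP 6.2 and 6.6.2.1. These conclusions come from the text alone and need no assumption.

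The size does rest on assumptions. For unequal reach of 95% against 75%, a plausible order is 2 to 4 points of a true 10 at SD 20, with power roughly halved at the stronger correlations. If reach is similar in both arms, bias is negligible under the model used, and the remaining cost is lost subjects.

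**What to change.** In SAP 6.6.2 item b, remove the condition on having reached 120% MT and define the summary fully:

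- **Subjects:** every mITT subject with at least one ramp-phase VAS score. Report the number of treated subjects with none.
- **Summary:** average the 3:45 and 18:45 scores within each ramp session, then average over that subject's ramp sessions up to target reached, end of session 5, or withdrawal.
- **Comparison:** by randomised first protocol, adjusted for gender, the stratification factor in SAP 4.1.
- **Beside it, by arm:** %MT achieved, number of ramp sessions, and withdrawals for discomfort.
- **Supportive comparison:** the 3:45 score at Treatment Visit 1 in all treated subjects. It precedes any scheduled escalation and starts from a common programmed intensity.

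The reacher-only comparison can stay as a supportive description if it is labelled as such.

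The cost is SAP wording only; no new data are needed. The new average will include subjects whose intensity stayed lower, and it still spans intensities and session counts that treatment can affect. It therefore restores the randomised comparison but does not measure comfort at equal intensity, which is why the accompanying summaries and the visit 1 score are needed. Withdrawal for discomfort can still be informative.

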### **6.6.2.1 Primary Analysis**

The majority of the primary efficacy endpoints will be assessed with the following hypothesis:

$H_0$ : Comfort Start Dash is equal to or inferior to Dash

$H_a$ : Comfort Start Dash is superior to Dash

Statistical Analysis Plan		Page 12 of 18
Sponsor Neuronetics	Study Comfort Start	Version 1.0

Note that some of the hypothesis testing will be two-sided, but the majority of inferential statistical testing will be looking at a one-sided alternative hypothesis that the treatment protocol with Comfort Start employed is superior to the Dash protocol without Comfort Start employed.

The endpoints will be evaluated using the mITT population.

The primary endpoints will be assessed via descriptive (unless otherwise specified) and superiority statistics.

### **6.6.3 Secondary Endpoints**

The secondary endpoints may be assessed via superiority or non-inferiority testing, with any non-inferiority margins to be defined, or may be assessed with descriptive summaries only.

The Secondary study outcomes will be determined as follows:

The ability to reach the prescribed treatment intensity, the time it takes to reach the prescribed intensity, maximum treatment intensity reached, subject treatment preference and discontinuations due to treatment discomfort between the two treatment protocols.

Once TMS therapy begins, adjustments to lower the stimulation intensity can begin immediately, as needed, for subject tolerance. The treater will assess if the subject can tolerate escalating the treatment MT by 10% at different time points. At each interval and the end of treatment, the treater will record the current %MT achieved. The goal will be to reach and sustain the target MT established by the treating physician of 120%MT. Once the target MT has been achieved and sustained for a certain period recording and increases of %MT may be discontinued but re-started at central intervals if %MT is subsequently reduced.

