9 CLINICAL SECTION

9.1 Introduction TMS and SoftStart

Repetitive transcranial magnetic stimulation (rTMS) is defined as the administration of a series of magnetic stimuli to the brain for the purpose of altering brain function. NeuroStar transcranial magnetic stimulation (TMS) Therapy was FDA cleared in 2008 for the treatment of major depressive disorder in adult patients who have not received benefit from prior medication. This procedure is non-invasive, does not require anesthesia, and may be delivered in an appropriately staffed outpatient setting. Although generally regarded as safe and without lasting adverse effects, patients treated with rTMS may experience minor side effects. The most common side effects are discomfort due to stimulation of the scalp musculature under the site of stimulation and muscle tension headaches which may persist for 1-2 hours post stimulation.^{8,9} These effects are thought to be due to the direct activation of muscles and nerves near the stimulating coil and both duration and intensity of stimulation impact the incidence of these effects.

Stimulus intensity is based on individually determined resting motor threshold (RMT or MT, minimum intensity to elicit muscle twitches at relaxed upper or lower extremities, by visual inspection or electromyography). The recommended stimulation intensity range is 110-120% MT.²¹ According to the original NeuroStar protocol, after determining the MT, a treatment session included stimulation at 120% motor threshold with a pulse sequence of 10 Hz for 4 seconds, followed by a 26 second inter-train interval (quiet period). A session lasted for a total of 37.5 minutes with a total of 3,000 pulses. A full NeuroStar treatment includes 30 daily sessions over 6 weeks with an additional 6 session ramp down over 3 weeks for a total of 9 weeks.¹⁵ In clinical practice, during the first 5-10 treatment sessions clinicians typically “ramp up” patients to the prescribed treatment intensity (% MT) to minimize side effects. Treatment sessions often start at 80-90% MT and stimulation intensity is increased to the prescribed level based on individual patient tolerance.

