10 STUDY DESIGN

10.1 General Description

This study is a prospective, randomized, single blind study to be conducted in 40 adults who have been prescribed treatment for MDD with rTMS. The study will be performed at a single site, where MDD patients, if eligible, may provide consent and participate. Prior to rTMS stimulation, the Motor Threshold (MT) will be established for each subject individually. Each subject will be evaluated for up to 2 weeks during their normal TMS treatment protocol, then exited from the study. The total study duration is expected to be approximately 6 months depending upon enrolment rate. The goal of the study is to monitor and compare patient comfort (treatment area sensitivity) using two different treatment protocols at the start of TMS

therapy where the stimulation intensity is typically escalated over 1-10 treatments until the patient is comfortable with the prescribed treatment dose (% MT; typically, 120%).

Each subject will be treated with rTMS for MDD as diagnosed and prescribed by their treating physician. All study visits will occur during the subject's normal pre-treatment evaluation and within the first 10 TMS treatment sessions. Study questionnaires will be administered during screening and during each treatment to evaluate the subject's perception of comfort specifically related to the TMS therapy provided that day.

Patients will be randomized after consent to receive either the standard Dash protocol (Treatment Y) or the modified Dash protocol with the SoftStart feature enabled (Treatment X). During all treatments, the subject will be blinded to whether they are receiving "Treatment X" or "Treatment Y".

Ramp Phase:

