Next, the PHQ-9 questionnaire will be completed, and subjects will have their Motor Threshold determined by the standard of care practice of the treating clinician and be randomized to receive their first rTMS stimulation with either treatment X or treatment Y.

The %MT treatment goal of 120% will be established by the physician. Subjects will have their Motor Threshold determined by the standard of care practice of the treating clinician and the first stimulation will be programmed to begin at 90% MT. Subjects will then be randomized to rTMS stimulation with either treatment X or treatment Y and have their first randomized stimulation treatment with the NeuroStar TMS Therapy System. Subject MT may be re-established and documented at the discretion of the treating physician at any time.

Treatment Assessments: Once TMS therapy begins, adjustments to lower the stimulation intensity can begin immediately, as needed, for subject tolerance. Every 3:45 minutes the TMS treater will assess if the subject can tolerate escalating the treatment MT by 10%. At each interval and the end of treatment, the treater will record the current %MT achieved. The goal will be to reach and sustain the target MT established by the treating physician of 120%MT. Once the target MT has been achieved and sustained for 3:45 minutes, recording and increases of %MT may be discontinued, but re-started at 3:45 minute intervals if %MT is subsequently reduced.

At minute 3:45, and at the end of the treatment session, the subject will be asked to complete a Visual Analog Scale (VAS), for Comfort/Pain.

If the subject reaches the prescribed %MT at Treatment Visit 1, the next study visit will be the start of the crossover phase of the study (Crossover Treatment 1), if not, they will continue to the next visit of the Ramp Phase.

Treatment Visits 2-5

Subjects will start treatment at the %MT established in the previous session and all study treatment procedures completed on Treatment Visit 1 will be repeated and documented for Treatment Visits 2-5. In addition, at the first time interval of 3:45, subjects will be asked a preference question - if they prefer the current treatment, last treatment, or if they cannot determine a difference. This question will be repeated at the end of the treatment visit.

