13.2 Discontinuation and Withdrawal of Subjects

Subjects may withdraw voluntarily from the study at any time. They may be withdrawn from the study by the Investigator if:

- A serious adverse event (SAE) occurs.
- The Investigator believes that for safety reasons it is in the best interest of the subject to be withdrawn.
- The subject withdraws consent.
- A positive urine drug screen at any visit.
- A positive pregnancy test at any visit; the subject reports pregnancy.
- Inability to locate and quantify a motor threshold as defined in the protocol or a motor threshold above 1.6 SMT.
- Investigator sets a treatment goal below 120% of MT.

Discontinuation information [e.g., date and the reason(s) for discontinuation] must be recorded in the subject's CRF (i.e., Study Termination Record page).

Follow-up information will be obtained for subjects who experience an SAE.

Subjects withdrawn from the study will not be replaced.

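### No baseline covariate, including motor threshold, is pre-specified for the between-arm ramp-phase comparisons; this gives up some precision if motor threshold is prognostic

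*SAP*

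**What the plan says.** Protocol 10.1 places the MT measurement ahead of treatment: "Prior to rTMS stimulation, the Motor Threshold (MT) will be established for each subject individually". Protocol 13.1 (Treatment Visit 1) describes MT determination before randomization, and the worksheet in Attachment A has a field for it. Protocol 9.1 explains that the stimulus is set relative to each patient's own MT, and says of scalp discomfort and headache that "both duration and intensity of stimulation impact the incidence of these effects".

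Two sets of comparisons set the starting arms against each other during the ramp phase.

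- SAP 6.6.2, analysis b, one of the candidate primary analyses, takes each patient's mean comfort score up to and including 120% MT: "then compare the average of the X averages (at most 20) to the average of the Y averages (at most 20". It is restricted to patients who reached 120%.
- SAP 6.6.3 lists the escalation outcomes: "The ability to reach the prescribed treatment intensity, the time it takes to reach the prescribed intensity, maximum treatment intensity reached".

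SAP 6.6.2 says that the methods "may include a t-test, Chi-Square test, and Fisher's Exact test", with a rank test as fallback. No analysis names MT or any other baseline variable as a covariate. Baseline variables are summarised descriptively (SAP 6.5), randomization is stratified by gender only (SAP 4.1), and the subgroup section does not mention MT (SAP 6.8).

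**The concern.** Because intensity is a percentage of the patient's own MT, two patients at the same %MT receive different absolute pulses under the coil, and the one with the higher MT receives the stronger pulse. If absolute intensity contributes to discomfort, as Protocol 9.1 suggests, MT is a plausible predictor of the ramp-phase comfort score and of how readily a patient escalates. It is a true baseline value and is already collected.

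With at most 20 patients per arm and no power calculation behind the sample size, inexpensive precision is worth having. If MT is prognostic, an unadjusted comparison leaves the variation it explains in the error term. The method wording is also open, so an MT adjustment could be chosen after the data are seen, in a trial where most tests are one-sided and treaters know the assignment.

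**Working it through.** There is no figure of the plan's own to reproduce: SAP section 5 gives N = 40 without power, effect size or standard deviation (SD).

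**Inputs.** N = 40, 20 per arm (SAP section 5; the upper limit for analysis b). r is the within-arm correlation between first MT and a patient's mean ramp-phase comfort score. Neither document gives r, so it is an assumption and is shown as a range.

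**Precision.** For a linear model with arm and one baseline covariate, against the unadjusted difference in means:

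variance ratio = (1 - r²) × (1 + 1/(N - 4)) = (1 - r²) × (1 + 1/36)

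The change in standard error (SE) is the square root of this ratio minus 1. The power column is one-sided at 0.05, for a true difference of 0.80 SD, at which the unadjusted t-test has 80% power.

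| Assumed r | Variance ratio | Change in SE | Power after adjustment |
|---|---|---|---|
| 0 | 1.028 | +1.4% | 79.0% |
| 0.1 | 1.017 | +0.9% | 79.4% |
| 0.2 | 0.987 | -0.7% | 80.4% |
| 0.3 | 0.935 | -3.3% | 82.2% |
| 0.5 | 0.771 | -12.2% | 88.2% |

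At r = 0.5 the gain is like having 40/0.771, or about 52, patients.

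**Break-even.** Setting the ratio to 1 gives r² = 1 - 36/37 = 1/37, so |r| is about 0.16. Below that, adjustment costs a little precision.

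**Fewer patients in analysis b.** If 15 per arm reached 120% (an assumption), N = 30 and the second factor is 1 + 1/26 = 1.038. The SE then changes by +1.9% at r = 0, -2.8% at r = 0.3 (√(0.91 × 1.038) = 0.972) and -11.7% at r = 0.5 (√(0.75 × 1.038) = 0.883). Break-even is √(1/27), about 0.19.

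**Chance imbalance.** Under simple 1:1 allocation the arm difference in mean MT has SE √(2/20) = 0.316 SD. The chance that it exceeds 0.3 SD in either direction is P(|Z| > 0.3/0.316) = 34%. Such an imbalance moves the unadjusted estimate by 0.3 × r outcome SDs: 0.09 SD at r = 0.3 and 0.15 SD at r = 0.5. No shift in millimetres is given, because the documents state no SD for the comfort scale.

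**Validity.** In simulation (3,000 trials per setting; r = 0, 0.3, 0.5) the unadjusted one-sided test at 0.05 rejected a true null in 4.7% to 5.0% of trials. The simulated variance ratios agreed with the formula.

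**The case against.** The strongest reply is that nothing here is wrong as planned. Randomization makes the unadjusted test valid, its standard error already allows for chance imbalance, and the simulated type I error is at its nominal level. That stands in full. A reader might infer that the planned comparison is biased, or that an MT imbalance invalidates it; the documents and the arithmetic do not support that.

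A reader might also infer that precision is certainly being lost. That does not follow either. Protocol 9.1 links intensity to side effects only qualitatively and does not say that MT predicts discomfort between patients. Several design features could weaken such a link. Dose is scaled to the individual. Intensity may be lowered at any time for intolerance, so scores are recorded at a tolerated level. Patients with "a motor threshold above 1.6 SMT" may be withdrawn, which narrows the range. Nor does the first MT fix every later intensity, since "Subject MT may be re-established and documented at the discretion of the treating physician at any time".

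The reach is limited as well. The other two candidate primary analyses average X and Y within each patient; if they are analysed as paired, a stable MT effect cancels. In analysis b, restriction to patients who reached 120% is a selection made after randomization, and adjusting for MT does not undo it. For reaching 120% and for time to 120% the linear SE figures do not apply; in a logistic model, for instance, adjustment changes the odds ratio being estimated. Maximum intensity moves in 10% steps towards a goal of 120%, so a linear model is doubtful there.

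Finally, the method list is permissive, secondary endpoints may be descriptive only, the trial is exploratory, and gender, the stratification factor, is not named as a covariate either. This shows that adjustment is unplanned, not excluded. It lowers the priority but does not remove the benefit of settling the covariate in advance. MT is singled out because the protocol itself supplies a mechanism for it.

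**Conclusion.** The point holds in a limited form and is minor. No baseline covariate is pre-specified for the ramp-phase between-arm comparisons, although MT is available before the first stimulation and is plausibly related to discomfort. The unadjusted analysis is sound. What is forgone is precision, and only if |r| exceeds about 0.16 at N = 40: about 3% of the SE at r = 0.3 and 12% at r = 0.5, against a cost of 1.4% at r = 0. These figures assume a linear model, 40 patients and a value of r that the documents do not give. They apply to the comfort comparison in SAP 6.6.2(b), where 40 is a best case. They do not extend to the binary and time-to-event endpoints in SAP 6.6.3.

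**What to change.** In SAP 6.6.2(b), pre-specify a linear model for each patient's mean ramp-phase comfort score with treatment arm and first MT as terms. Define first MT as the value measured before the first stimulation, not a later re-determination. Keep the unadjusted comparison as a sensitivity analysis.

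For reaching 120%, time to 120% and maximum intensity in SAP 6.6.3, describe any MT-adjusted analysis as supportive only.

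The cost is a sentence or two of SAP wording and no new data. Statistically it is one degree of freedom, or about 1.4% on the SE at N = 40 if MT predicts nothing.
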